10.5 Interim Analysis and Data Monitoring

No formal interim analyses will be performed; however, the Dermavant study team may review PK and safety data on an ongoing basis. This includes an analysis of the PK data after 25% of the subjects (n=9) have completed the study to re-assess the PK sampling scheme with the potential to eliminate the 5-hour post-dose blood draw. If required, changes to the protocol will be made through a protocol amendment.

10.6 Examination of Subgroups

Efficacy endpoints will be summarized by age group (2-6 yrs, 7-11 yrs, and 12-17 yrs) and overall.

10.7 Multiple Comparison/Multiplicity

Not applicable.

10.8 Multicenter Studies

There will be approximately 12 study sites in the United States (US) and Canada. Efficacy data will not be summarized by site; however, study sites will be identified in data listings.

11. METHODS OF EFFICACY ANALYSIS

11.1 Efficacy Analyses

All efficacy analyses will be performed based on the safety population. The efficacy endpoints will be summarized descriptively by age group (2-6 yrs, 7-11 yrs, and 12-17 yrs) and overall.

Categorical endpoints include:

- Proportion of subjects who have a vIGA-AD™ score of clear or almost clear (0 or 1) and at least a 2-grade reduction from Baseline at each study visit,
- Proportion of subjects with $\geq 50\%$ improvement in EASI score from Baseline at each study visit,
- Proportion of subjects with $\geq 75\%$ improvement in EASI score from Baseline at each study visit,
- Proportion of subjects with $\geq 90\%$ improvement in EASI score from Baseline at each study visit,
- Proportion of subjects with a Baseline PP-NRS score ≥ 4 who achieve ≥ 4 -point reduction in the average weekly PP-NRS from Baseline at each study visit,
- Proportion of subjects ≥ 12 years old with a Baseline PP-NRS score ≥ 4 who achieve a ≥ 4 -point reduction in the average weekly PP-NRS from Baseline at each study visit,
- Proportion of subjects 2 to < 12 years old with a Baseline PP-NRS score ≥ 4 who achieve a ≥ 4 -point reduction in the average weekly PP-NRS from Baseline at each study visit,

Continuous endpoints include:

- Change in vIGA-AD™ score from Baseline at each study visit,
- Mean change and percent change in EASI score from Baseline at each study visit,
- Mean change and percent change in %BSA affected from Baseline at each study visit,
- Mean change and percent change in %BSA x vIGA-AD™ from Baseline at each study visit
- Mean change in average weekly PP-NRS score from Baseline at each study visit by age group.

Categorical endpoints will be summarized by presenting counts and percentages of subjects in corresponding categories. Percentages for missing values are omitted and do not account for the percent calculation of other categories.

Continuous endpoints will be summarized by presenting the number of observations, means, standard deviations, medians, minimums, and maximums.

12. PHARMACOKINETIC ANALYSES

All pharmacokinetic analyses will be performed using a validated installation of Phoenix WinNonlin®, Version 8.1 or above (Certara, Princeton, NJ USA) as part of a 21 CFR Part 11 compliant database system (Phoenix Knowledgebase Server “PKS”) and all the analyses will be stored on the PKS, with an audit trail for all the steps capturing the changes needed to finish the analysis.

Concentrations of tapinarof and tapinarof sulfate will be determined in plasma samples using a validated bioanalytical method. Raw data will be archived at the bioanalytical site. From the plasma concentration time data on Day 1 (1, 3-, and 5-hours post-dose), the following primary PK parameters will be determined, if data permit: AUC_{0-t} , C_{max} , $C\tau$, T_{max} , and T_{last} .

Analyses of the PK data will be performed after 25% of the subjects (n=9) have completed the study to re-assess the PK sampling scheme with the potential to eliminate the 5-hour post-dose blood draw. If required, changes to the protocol will be made through a protocol amendment. This analysis will be performed by Dermavant and is not considered to be a formal PK analysis.

12.1 Data Handling

Blood samples will be collected at Screening (to serve as the Baseline pre-dose sample), on Day 1 at 1, 3, and 5-hours post-dose and a single pre-dose sample on Day 28.

The raw plasma concentration data will be handled as follows:

For summary tables and figures for plasma concentrations:

1. The planned sampling time will be used in summary tables and the actual sampling times will be used for all figures of individual concentrations.
2. All concentration values < lower limit of quantification (BQL) will be set to zero.
3. Missing values will not be replaced.

For determination of PK metrics:

1. Actual sampling time will be used.
2. Concentration values <BQL before T_{max} will be set to zero. Therefore, a subject with BQL values for the entire sampling period will have a C_{max} of zero.
3. Concentration values <BQL that occur after a measurable concentration and followed by a value above the BQL will be set to missing.
4. Concentration values <BQL that occur at the end of the collection interval (after the last quantifiable concentration) will be set to missing.
5. Missing values will not be replaced.

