5. DETERMINATION OF SAMPLE SIZE

Approximately 36 subjects ages 2 to 17 years old will be enrolled in the study with approximately 12 subjects, and a minimum of 10 subjects, enrolled into each of the three following age cohorts: 2-6 years old, 7-11 years old, 12-17 years old.

There is no formal statistical hypothesis planned and the sample size is mainly based on feasibility and an estimated number of subjects needed to address the objectives of the study.

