8. ANALYSIS SETS

The safety population will include all enrolled subjects who receive at least 1 application of study drug. Subjects will be analyzed as treated. The safety population will be used for efficacy and safety analyses.

The PK population will include all subjects who undergo plasma PK sampling and have at least one evaluable concentration-time data available for analysis. A sample that is below the quantification limit (BQL) of the assay is considered evaluable. Subjects will be analyzed as treated.

The number of subjects screened, number enrolled, and the number of subjects in each population will be summarized.

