12.3 Determination and Analysis of PK Parameters

Full precision concentration data and actual sample times will be used for the determination of all PK parameters.

Raw plasma concentrations for the derivation of pharmacokinetic parameters will be handled as described in Section 12.1.

The following PK parameters will be derived, based on available data:

- C_{max} (pg/mL) – maximum observed concentration
- T_{max} (hr) – time of the maximum observed concentration
- $C\tau$ (pg/mL) – last quantifiable concentration determined directly from individual concentration-time data
- T_{last} (hr) – time of the last quantifiable concentration
- AUC_{0-t} (pg•hr/mL) – area under the concentration-time curve from time zero to the last quantifiable concentration, calculated using a linear trapezoidal rule that includes summation from the time of the first measurable concentration to the time of the last measurable concentration as follows:

$$AUC_{0-t} = \sum_{i=1}^{n-1} \left[\frac{C_{i+1} + C_i}{2} (t_{i+1} - t_i) \right]$$

Where C_i is the i -th sample, t_i is the time of the i -th sample from dosing, and n is the number of available samples up to and including the final quantifiable concentration.

AUC values will be estimated using the linear-up, log-down method. A minimum of 3 data points are required for determination of an AUC.

The PK parameters as listed above will be obtained by non-compartmental analysis.

Individual PK parameters:

A raw data listing will be provided displaying the individual PK parameters. Results will be displayed using 3 significant digits.

Summary statistics of PK parameters:

Pharmacokinetic parameters (except T_{last} and $C\tau$) will be summarized using descriptive statistics (n , arithmetic mean, SD, CV % for the arithmetic mean, median, minimum, maximum, geometric mean, and CV % for the geometric mean). The geometric mean and CV % for the geometric mean will not be calculated for T_{max} . Results will be displayed using 3 significant digits.

Summary statistics of PK parameters will be determined by age group and overall. PK parameters of C_{max} and AUC_{0-t} will also be normalized to %BSA at Baseline by dividing each parameter by cm^2 of BSA of disease. For this calculation, 1% BSA is equal to 185 cm^2 .

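### A child with all Day 1 samples below quantification counts as zero for Cmax but has no AUC0-t under SAP 12.3, so the AUC0-t summaries omit the lowest exposures

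*SAP*

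**What the plan says.** SAP 8 keeps an all-BQL child in the PK population: "A sample that is below the quantification limit (BQL) of the assay is considered evaluable".

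SAP 12.1 schedules sampling at Screening (serving as pre-dose), then "on Day 1 at 1, 3, and 5-hours post-dose and a single pre-dose sample on Day 28". For the PK metrics it sets BQL values before Tmax to zero and draws the consequence for Cmax: "Therefore, a subject with BQL values for the entire sampling period will have a C_{max} of zero". For trailing values the rule differs: "Concentration values <BQL that occur at the end of the collection interval (after the last quantifiable concentration) will be set to missing". Missing values are not replaced.

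SAP 12.3 defines AUC0-t as the "area under the concentration-time curve from time zero to the last quantifiable concentration". The n in its formula counts samples only as far as the final quantifiable one. It then adds: "A minimum of 3 data points are required for determination of an AUC".

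Cmax and AUC0-t are both listed as primary PK parameters in SAP 12, subject to the data permitting. SAP 12.3 summarises both by age group and overall, with arithmetic and geometric statistics, and normalises both to BSA. No section gives an AUC0-t value for an all-BQL child, and none says how a zero enters a geometric mean.

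**The concern.** The sponsor foresaw the all-BQL profile and settled it for one exposure measure only. Followed literally, the rules put the same child into the Cmax table with a value of zero and leave that child out of the AUC0-t table. The AUC0-t is absent because exposure was low, so the remaining children are selected on the outcome being summarised.

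The consequence falls mainly on the age-cohort comparison. If one cohort has more all-BQL children than another, its mean and median AUC0-t are raised more, and a real difference between cohorts looks smaller. Cmax and AUC0-t may also differ across cohorts partly because they describe different children. The same applies to the BSA-normalised values and to the plots against baseline %BSA and grams applied.

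**Working it through.** **Inputs.** About 36 children, about 12 per cohort (SAP 5). Day 1 samples at 1, 3 and 5 h plus a Screening sample used as pre-dose (SAP 12.1), assumed here to be BQL. There is no power or alpha figure to reproduce: "There is no formal statistical hypothesis planned and the sample size is mainly based on feasibility".

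**Step 1: apply the rules to every pattern.** Write B for BQL and Q for quantifiable at 1, 3 and 5 h. SAP 12.3 does not define a data point, so two readings are counted: (A) quantifiable values only; (B) available samples up to the last quantifiable one, including the pre-dose zero and leading BQL zeros.

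| Pattern | Cmax | Points, A | Points, B | AUC0-t under A / B |
|---|---|---|---|---|
| BBB | 0 | 0 | 0 | no / no |
| QBB | > 0 | 1 | 2 | no / no |
| BQB | > 0 | 1 | 3 | no / yes |
| QQB | > 0 | 2 | 3 | no / yes |
| QBQ | > 0 | 2 | 3 | no / yes |
| BBQ | > 0 | 1 | 4 | no / yes |
| BQQ | > 0 | 2 | 4 | no / yes |
| QQQ | > 0 | 3 | 4 | yes / yes |

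The plan's one stated figure, Cmax = 0 for BBB, reproduces. BBB and QBB have no AUC0-t under either reading. In QBB the 3 h and 5 h values become missing, leaving the pre-dose zero and the 1 h value. If the 5 h draw were dropped, reading A would give no child an AUC0-t, and reading B would still lose BB and QB.

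**Step 2: effect on the arithmetic mean.** With k all-BQL children among N, the mean over the remaining N - k divided by the mean with zeros entered is N/(N - k) = 1/(1 - q), where q = k/N. For N = 12: k = 1 gives 12/11 = 1.09; k = 2 gives 12/10 = 1.20; k = 3 gives 12/9 = 1.33; k = 4 gives 12/8 = 1.50. For N = 36, k = 9 gives 36/27 = 1.33. These factors are relative to the zero convention, not to true exposure.

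**Step 3: effect relative to true exposure (assumed model).** Let AUC be lognormal with geometric CV g of 80%, 120% or 200%, so s = sqrt(ln(1 + g²)) = 0.703, 0.944 or 1.269. Let the lowest fraction q of a cohort be all-BQL, and let z be the normal quantile of q.

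- Mean with exclusion / true mean = Φ(s - z)/(1 - q).
- Mean with zeros / true mean = Φ(s - z).
- Exclusion moves the median to the (1 + q)/2 percentile. It is overstated by 9-17% at q = 10% and 25-50% at q = 25%.

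Now let a second cohort have twice the exposure with the same CV and quantification limit. Its all-BQL share is q' = Φ(z'), with z' = z - ln 2/s. The reported ratio under exclusion is 2 × [Φ(s - z')/(1 - q')] / [Φ(s - z)/(1 - q)].

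Example, g = 120%, q = 25%: z = -0.674 and Φ(1.618)/0.75 = 1.263; z' = -1.409, q' = 0.080 and Φ(2.353)/0.920 = 1.076; ratio = 2 × 1.076/1.263 = 1.70.

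| q, lower cohort | q', higher cohort | Exclusion / true mean | Zeros / true mean | True ratio 2.0, reported under exclusion | Reported with zeros |
|---|---|---|---|---|---|
| 10% | 1-3% | 1.085-1.105 | 0.976-0.995 | about 1.86 | 2.01-2.05 |
| 25% | 5-11% | 1.22-1.30 | 0.92-0.97 | about 1.7 | 2.04-2.16 |
| 40% | 11-21% | 1.38-1.56 | 0.83-0.94 | about 1.6 | 2.10-2.35 |

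Ranges run over the three CVs. Neither convention is unbiased; zeros are closer to the true mean in every row.

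**The case against.** The SAP nowhere prints that an all-BQL child has no AUC0-t. SAP 12.1 sets BQL values to zero and carries that through to Cmax; a programmer who kept those zeros as data points would have at least three and would output an area of zero. That is possible, but it conflicts with the SAP 12.3 end point and with its count of n. If two outputs are plausible, the rule needs stating.

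The plan also limits and partly exposes the problem. It reports n for each parameter by age group, lists individual parameters, and counts BQL samples by subject and overall. Concentration summaries set every BQL value to zero, mean Day 1 profiles are shown by age group, and Cmax keeps these children. There is no hypothesis test, parameters are derived only if the data permit, and a maximal use study looks mainly for high exposure. All of this stands. It makes the mismatch visible and lowers the stakes, but it does not correct the AUC0-t summaries.

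The size is open. Protocol 1.2 places the highest plasma concentrations in the first week of treatment, which argues against a large all-BQL share on Day 1 without excluding it.

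A reader might infer more: that a 40% all-BQL share in one cohort would shrink a twofold difference to 2.0/(1/0.6) = 1.2. The documents do not support this. It treats BQL exposure as exactly zero, and it pairs 40% with 0% all-BQL, whereas a shared quantification limit and equal CV would put the higher cohort at 11-21%. Nor does it follow that both parameters should be restricted to identical children, since that would discard real Cmax values from children quantifiable only at 1 h.

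**Conclusion.** The concern holds as a gap between SAP 12.1 and SAP 12.3. That an all-BQL child has no AUC0-t is an inference from the definition and the three-point minimum, but the only one consistent with that text. Arithmetic mean and median AUC0-t then omit the lowest exposures and describe fewer children than Cmax.

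The error in the mean is upward, so overall exposure is overstated rather than understated, and omitting all-BQL children cannot change the maximum. What suffers is the comparison between age cohorts: under the assumed lognormal model a true twofold difference would be reported as about 1.86, 1.7 or 1.6 when the lower-exposure cohort has 10%, 25% or 40% all-BQL children. These shares are assumptions. For geometric means the mismatch is undetermined, because a zero Cmax has no logarithm and the SAP has no rule for it.

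**What to change.** In SAP 12.3:

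- Set AUC0-t to zero when all post-dose Day 1 samples are BQL, matching the Cmax rule.
- State whether the pre-dose zero and leading BQL zeros count as data points towards the minimum of three.
- Report per cohort the number of all-BQL children and the number with a Cmax but no calculable AUC0-t.
- Compute geometric statistics for both parameters on non-zero values, with that n stated.

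The cost is a few sentences and a table footnote; no new data are needed. The median becomes correct as long as fewer than half the children are all-BQL. The downside is that mean AUC0-t falls, and is somewhat understated, where all-BQL profiles occur (0.83 to 0.995 of the true mean in the model above), and a cohort ratio is then somewhat overstated. Children quantifiable only at 1 h would still lack an AUC0-t, which is why their number should be shown.

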12.2 Presentation of Plasma Concentrations

Individual plasma concentration results:

A raw data listing will be provided displaying the concentration as reported and the nominal and actual sampling times relative to start of dose administration (time since last dose). Results will be displayed using 3 significant digits.

Summary statistics of plasma concentrations:

The plasma concentrations for each analyte (i.e., tapinarof, tapinarof sulfate) will be summarized by nominal time point on Day 1 and Day 28 using descriptive statistics (n, arithmetic mean, standard deviation (SD), coefficient of variation (CV) % of arithmetic mean, median, minimum, maximum, geometric mean, and CV % for the geometric mean). The number of plasma concentrations that are BQL will be summarized by subject and the number and percentage of plasma concentrations that are BQL will be summarized overall.

Results will be displayed using 3 significant digits.

The CV % for the geometric mean will be calculated using the following formula:

$$CV (\%) = 100 * \sqrt{e^{SD^2} - 1}$$

where SD = standard deviation of the natural-log transformed data.

Figures:

Individual and mean concentration-time profiles on Day 1 will be provided on linear and semilogarithmic scales and may be presented with or without error bars. For individual concentration-time profiles, the actual sampling times will be used. Mean concentration-time profiles will be provided by age group and overall.

Overlaid individual and mean concentration-time plots on Day 1 for tapinarof and tapinarof sulfate will be provided in linear and semi-log scales.

Figures will be provided for the following relationships:

- Baseline %BSA of disease (x-axis) and Day 1 C_{max} (y-axis)
- Baseline %BSA of disease (x-axis) and Day 1 AUC_{0-t} (y-axis)
- Average grams of study drug administered per day (x-axis) and Day 1 C_{max} (y-axis)
- Average grams of study drug administered per day (x-axis) and Day 1 AUC_{0-t} (y-axis)
- Day 1 C_{max} (x-axis) and Day 1 C_{max} normalized by BSA (y-axis)
- Day 1 AUC_{0-t} (x-axis) and Day 1 AUC_{0-t} normalized by BSA (y-axis)

12.3 Determination and Analysis of PK Parameters

Full precision concentration data and actual sample times will be used for the determination of all PK parameters.

Raw plasma concentrations for the derivation of pharmacokinetic parameters will be handled as described in Section 12.1.

The following PK parameters will be derived, based on available data:

- C_{max} (pg/mL) – maximum observed concentration
- T_{max} (hr) – time of the maximum observed concentration
- $C\tau$ (pg/mL) – last quantifiable concentration determined directly from individual concentration-time data
- T_{last} (hr) – time of the last quantifiable concentration
- AUC_{0-t} (pg•hr/mL) – area under the concentration-time curve from time zero to the last quantifiable concentration, calculated using a linear trapezoidal rule that includes summation from the time of the first measurable concentration to the time of the last measurable concentration as follows:

$$AUC_{0-t} = \sum_{i=1}^{n-1} \left[\frac{C_{i+1} + C_i}{2} (t_{i+1} - t_i) \right]$$

Where C_i is the i -th sample, t_i is the time of the i -th sample from dosing, and n is the number of available samples up to and including the final quantifiable concentration.

AUC values will be estimated using the linear-up, log-down method. A minimum of 3 data points are required for determination of an AUC.

The PK parameters as listed above will be obtained by non-compartmental analysis.

Individual PK parameters:

A raw data listing will be provided displaying the individual PK parameters. Results will be displayed using 3 significant digits.

Summary statistics of PK parameters:

Pharmacokinetic parameters (except T_{last} and $C\tau$) will be summarized using descriptive statistics (n , arithmetic mean, SD, CV % for the arithmetic mean, median, minimum, maximum, geometric mean, and CV % for the geometric mean). The geometric mean and CV % for the geometric mean will not be calculated for T_{max} . Results will be displayed using 3 significant digits.

Summary statistics of PK parameters will be determined by age group and overall. PK parameters of C_{max} and AUC_{0-t} will also be normalized to %BSA at Baseline by dividing each parameter by cm^2 of BSA of disease. For this calculation, 1% BSA is equal to 185 cm^2 .

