1.1.2 Study Rationale

This Phase 2a maximal use study is being conducted as part of a clinical development program to evaluate the safety and systemic exposure of tapinarof cream, 1% for the topical treatment of AD in subjects ages 2 to 17 years. Maximal use trials enroll subjects with the disease under study and who generally have more severe disease or with a large BSA of affected skin who might be more susceptible to systemic AEs. The purpose of these studies is to evaluate systemic exposure under conditions that would maximize the potential for drug absorption with the intended use of the product [Bashaw, 2014]. The results of this study are intended to support product registration in the United States and Canada.

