4.2 Inclusion Criteria

Each subject must meet all of the following criteria to be eligible to participate in the study:

1. Male and female subjects ages 2 to 17 years with a clinical diagnosis of AD by Hanifin and Rajka criteria [[Hanifin, 1980](#)] (see [Appendix 1](#)).
2. Subjects with AD covering $\geq 25\%$ of the BSA for subjects ages 12-17 years old, or $\geq 35\%$ of the BSA for subjects ages 2-11 years old, suitable for topical therapy. Scalp should be excluded from the BSA calculation to determine eligibility during Screening and at Baseline, and for all efficacy assessments.
3. A vIGA-AD™ score of 3 or greater at Screening and Baseline (pre-dosing).
4. AD present for at least 6 months for subjects ages 6-17 years old or 3 months for subjects ages 2 to 5 years old, confirmed by prior medical documentation and/or according to the subject and/or caregiver(s).
5. Female subjects of childbearing potential who are engaging in sexual activity that could lead to pregnancy should use one of the following acceptable birth control methods while on study and for 4 weeks after the last exposure to study drug.
 - Acceptable contraception methods include intrauterine device, hormonal contraceptives, barrier method (e.g., condom or diaphragm), or surgical sterilization of male partner (vasectomy)
 - Subjects who claim abstinence as their method of contraception are allowed provided they agree to use a barrier method (e.g., condom or diaphragm) should they become sexually active from Screening to 4 weeks after the last dose of study drug
 - Non-child-bearing potential is defined as:
 - premenarchal
 - pre-menopausal females with a documented bilateral tubal ligation, bilateral oophorectomy, hysterectomy, or hysteroscopic sterilization
6. Female subjects of childbearing potential must have a negative serum pregnancy test at Screening and a negative urine pregnancy test at Baseline (Day 1).
7. Subject, subject's parent(s), or legal representative must be capable of giving written informed consent, which includes compliance with the requirements and restrictions listed in the consent/assent form; written informed consent must be obtained prior to any study related procedures.

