6.3.2 Brief Physical Examination

A brief physical examination will include, at a minimum, assessments of the skin, lungs, cardiovascular system, and abdomen (liver and spleen). Assess for changes in onset of menses (female participants) or sexual activity (male or female participants). Determine if there is a need for contraception or barrier use. Height and weight will be measured at Screening only. Investigators should pay special attention to clinical signs related to previous serious illness.

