Appendix 4: Calculation of Percent Body Surface Area Affected and Eczema Area Severity Index

Calculation of %BSA Affected:

Note: At Screening, Baseline and for all efficacy assessments, lesions on the scalp will not be included in the calculation of %BSA affected as these areas will not be included in the efficacy analyses.

Measurement of involved BSA is estimated by the handprint method: the total palmar surface of the subject's palm and digits is approximately 1% of their total BSA.

Estimate the involved regional area by determining the number of "full" handprints plus the number of handprints covered if several smaller lesions are "pushed together."

For subjects ages 8 years and above the maximum involvement by region is as follows:

- Head and neck = 10% of overall BSA (10 handprints);
1 hand-sized lesion ~ 10% of head and neck area
- Arms/Upper extremities = 20% of overall BSA (20 handprints);
1 hand-sized lesion ~ 5% of the upper extremities
- Trunk (including axillae and groin) = 30% of overall BSA (30 handprints);
1 hand-sized lesion ~ 3.33% of the trunk
- Legs/Lower extremities (including buttocks) = 40% of overall BSA (40 handprints);
1 hand-sized lesion ~ 2.5% of the lower extremities

For subjects ages <8 years the maximum involvement by region is as follows:

- Head and neck = 20% of overall BSA (20 handprints);
1 hand-sized lesion ~ 5% of head and neck area
- Arms/Upper extremities = 20% of overall BSA (20 handprints);
1 hand-sized lesion ~ 5% of the upper extremities
- Trunk (including axillae and groin) = 30% of overall BSA (30 handprints);
1 hand-sized lesion ~ 3.33% of the trunk
- Legs/Lower extremities (including buttocks) = 30% of overall BSA (30 handprints);
1 hand-sized lesion ~ 3.33% of the lower extremities

Table 6. Calculation of Percent Body Surface Area Affected

Body Region	Number of Handprints for Each Region
Head and neck	
Arms/upper extremities	
Trunk	
Legs/lower extremities	
TOTAL Involved %BSA – sum of handprints for each region	

Note: Shaded cells will be calculated in the CRF.

%BSA = percent body surface area; CRF = case report form

Calculation of EASI score (scalp excluded)

Four anatomic sites – head, upper extremities, trunk, and lower extremities – are assessed for erythema, edema/papulation, excoriation and lichenification as seen on the day of the examination. The severity of each sign is assessed using a 4-point scale, half points may be used (e.g. 0.5, 1.5, 2.5):

- 0 = None (Absent)
- 1 = Mild

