- Legends will be used for all figures with more than 1 variable or item displayed. Subject count (n=xx) will be included, as appropriate.
- Figures will be in black and white but can be in color to add value to the clarity and readability of a figure. Lines must be wide enough to see the line after being copied.
- The last footnotes will be
 - “Source: xxx”, where xxx indicates the source listing number(s) and/or source dataset(s) (eg, ADaM).
 - “PROGRAM SOURCE: ...\\xx.sas DDMMMYY hh:mm”.

Listings

- If not otherwise specified, all data listings will be sorted by subject number, visit, and date/time, as appropriate.
- All date values will be presented in a SAS date (eg, 29AUG2001) format.
- All observed time values will be presented using a 24-hour clock HH:MM:SS format (eg, 01:35:45 or 11:26). Seconds will only be reported if they were measured as part of the study.
- The last footnote will be
 - “PROGRAM SOURCE: ...\\xx.sas DDMMMYY hh:mm”.

Standard Calculations

Variables requiring calculation will be derived using the following formulas:

- **Days** – A duration expressed in days between 1 date (date1) and another later date (date2) is calculated using the formulas noted below:
duration in days = date2 – date1 + 1
- **Months** – A duration expressed in months is calculated using the INTCK function of SAS as follows: months=intck('month','date1'd,date2'd, 'continuous').
- **Years** – A duration expressed in years between one date (date1) and another later date (date2) is calculated as follows:
duration in years = intck('year', 'date1'd, 'date2'd, 'continuous').
- **Age** – will be reported in EDC based on informed consent date
- **Height** – Height entries made in inches (in) are converted to centimeters (cm) using the following formula:
height (cm) = height (in) × 2.54.
- **Weight** – Weight entries made in pounds (lb) are converted to kilograms (kg) using the following formula:
weight (kg) = weight (lb)/2.2046.
- **Temperature** – Temperature entries in degrees Fahrenheit are converted to degrees centigrade using the following formula:
temp (degrees centigrade) = 5/9 × [temp (degrees Fahrenheit) – 32].

- **Body Mass Index (BMI)** – BMI is calculated using height (cm) and weight (kg) using the following formula:
$$\text{BMI (kg/m}^2\text{)} = \text{weight (kg)}/[\text{height (cm)}/100]^2\text{].}$$
- **Change from baseline** – Change from baseline will be calculated as:
$$\text{Change} = \text{post-baseline value} - \text{baseline value}.$$

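### SAP 12.3 converts diseased %BSA to cm² at a fixed 185 cm² per 1% for all ages 2 to 17, so Cmax and AUC0-t per cm² are mis-scaled by body size, most in the youngest cohort

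*SAP*

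**What the plan says.** SAP 12.3 adds a normalised version of Cmax and AUC0-t. Each parameter is divided by the cm² of diseased skin at Baseline, obtained from %BSA with a single constant: "For this calculation, 1% BSA is equal to 185" cm². The SAP gives no source for the constant, and neither document ties it to age or size. The same section states "Summary statistics of PK parameters will be determined by age group and overall", the age groups being 2-6, 7-11 and 12-17 years. SAP 12.2 plots Day 1 Cmax and AUC0-t against their versions "normalized by BSA (y-axis").

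Protocol Appendix 4 defines the percentage differently. One handprint of the subject's own "palm and digits is approximately 1% of their total BSA", so 1% is a share of that child's body and not a fixed area. Protocol 6.2.1.2 uses the same convention.

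The data for an individual area are available. Protocol 6.3.2 says "Height and weight will be measured at Screening only", and SAP Appendix A already puts both into metric units: "BMI is calculated using height (cm) and weight (kg) using the following formula". The SAP derives no total body surface area.

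**The concern.** A constant of 185 cm² gives a 2-year-old and a 17-year-old the same skin area. The resulting quantity is Cmax/%BSA or AUC0-t/%BSA divided by a fixed number. It adjusts for the percentage of skin affected but contains no information on body size, although its unit says it does.

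At stake is the reading of the normalised values across cohorts. Protocol 1.2 rests extrapolation down to age 2 partly on similarity of skin development and pharmacokinetics. A reader testing that idea with a per-cm² table would be comparing numbers whose scale error is largest in the youngest children and runs towards understatement.

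**Working it through.** **Inputs.** From the documents: 185 cm² per 1% BSA (SAP 12.3); 1% defined by the subject's handprint (Protocol Appendix 4); a 35% BSA entry minimum for ages 2-11 (Protocol 4.2). Heights and weights are **assumed**, because the documents give none. Total BSA is taken from the Mosteller formula, √(cm × kg / 3600) in m².

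**Area implied by the SAP.** 185 × 100 = 18,500 cm² = 1.85 m² for every subject. The documents give no derivation of 185, so there is no calculation to reproduce.

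**Error factor.** For a subject with total BSA *S* m², 1% is 100 × *S* cm².

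- SAP value = Cmax / (%BSA × 185)
- True value = Cmax / (%BSA × 100 × *S*)
- SAP / true = *S* / 1.85, so the understatement factor is 1.85 / *S*

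Cmax and %BSA cancel, and the same holds for AUC0-t. The value is too low when *S* is below 1.85 and too high when it is above.

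**Size on assumed bodies.**

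| Cohort | Height / weight | *S* (m²) | 1.85 / *S* |
|---|---|---|---|
| 2-6 | 82 cm / 10 kg | 0.477 | 3.88 |
| 2-6 | 115 cm / 20.5 kg | 0.809 | 2.29 |
| 2-6 | 122 cm / 28 kg | 0.974 | 1.90 |
| 7-11 | 112 cm / 18 kg | 0.748 | 2.47 |
| 7-11 | 133 cm / 28 kg | 1.017 | 1.82 |
| 7-11 | 155 cm / 55 kg | 1.539 | 1.20 |
| 12-17 | 138 cm / 30 kg | 1.072 | 1.73 |
| 12-17 | 162 cm / 50 kg | 1.500 | 1.23 |
| 12-17 | 172 cm / 65 kg | 1.762 | 1.05 |
| 12-17 | 185 cm / 95 kg | 2.210 | 0.84 (printed value 1.19 times true) |

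Mid-size children aged 2 to 6 fall at about 2.3 to 3.4 (87 cm / 12.5 kg gives 0.550 m² and 3.37). The Haycock formula gives nearly the same factors: 1.89 instead of 1.90 at 122 cm / 28 kg, and 3.89 instead of 3.92 at 80 cm / 10 kg.

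**Effect on a comparison.** If subjects of 0.809 and 1.500 m² had equal true per-cm² values, the smaller child's would print lower by 1.500 / 0.809 = 1.85, about 1.9-fold. Conversely, a hypothetical Cmax of 1000 pg/mL at 40% BSA prints as 1000 / (40 × 185) = 0.135 pg/mL per cm² for any child. The true value is 1000 / (40 × 55) = 0.455 at 0.55 m² and 1000 / (40 × 81) = 0.309 at 0.81 m².

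**Plausibility check.** The 35% minimum applies to BSA "of the BSA for subjects ages 2-11 years old, suitable for topical therapy". At that minimum the SAP area is 35 × 185 = 6,475 cm². That exceeds the whole skin of any child below 0.6475 m². The 82 cm / 10 kg child has about 4,770 cm² in total, of which 35% is about 1,670 cm².

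**The case against.** The strongest reply is that this is a unit label, not a damaged analysis. SAP 12.3 describes its aim as normalising to %BSA. Dividing by a constant as well leaves every ratio between subjects as it would be per 1% BSA, and a reader can undo it by multiplying by 185. That is true, and it is why relabelling is an adequate fix. It does not rescue the table as planned, which states a unit its numbers do not have.

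Second, true per-cm² values may not be a better basis for comparing ages, because plasma concentration itself depends on body size. Suppose absorption per cm² is equal and distribution volume is proportional to weight. Then Cmax per cm² would be 50 / 20.5 = 2.4-fold higher in the 20.5 kg child than in the 50 kg one, while Cmax per 1% BSA would differ by only (0.809 / 20.5) / (1.500 / 50) = 1.3-fold. This stands as a caution about interpretation: the two fixes give different cohort patterns, and each is right only for its own label.

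Third, the fold figures rest on assumed sizes, 3.9 belongs to a very small 2-year-old, and the cohorts' ranges overlap. All of that stands. The relation *S* / 1.85 does not depend on the assumed sizes.

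Fourth, the consequence is limited. The normalised parameters are not protocol endpoints and nothing is tested. The stated purpose, to "evaluate systemic exposure under conditions that would maximize the potential for drug absorption", is served by the raw values. That stands too, and it limits how serious the point is.

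**Conclusion.** The concern holds. As written, SAP 12.3 prints wrong per-cm² values for any subject whose total BSA is not close to 1.85 m², and nothing in either document justifies or limits the constant. The form of the error is exact. Its size depends on the assumed heights and weights: about 1.9- to 3.9-fold too low at ages 2-6, 1.2- to 2.5-fold too low at ages 7-11, and from 1.7-fold too low to 1.19 times the true value at ages 12-17.

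The effect is confined to the normalised Cmax and AUC0-t summaries and the two normalised figures. Raw Cmax, raw AUC0-t, Day 28 concentrations and the plots against Baseline %BSA and grams used do not change. It should be corrected before these outputs are produced, but it does not threaten the primary PK results.

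**What to change.** Decide which quantity is wanted and make the number match its unit, in the normalised summaries and both figures.

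- **If per cm² is wanted**, replace the last sentence of SAP 12.3 with: *Diseased area (cm², scalp excluded) = Baseline %BSA / 100 × total BSA, where total BSA (cm²) = 10,000 × √(Screening height in cm × Screening weight in kg / 3600).*
- **If an adjustment for percentage affected is enough**, delete the 185 cm² conversion and label the values as per 1% BSA affected. This is simpler and equally valid.

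The cost is one SAP sentence and at most one derived variable. Direct comparability with any study reported on the 185 cm² scale would be lost; a labelled secondary column can keep it. Raw Cmax and AUC0-t by age group should remain the main display, because per-cm² plasma values still carry body size. Scalp lesions may be treated (Protocol 5.1.5) but lie outside %BSA, so neither option includes that area; a footnote should say so.
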